6.14. Bioanalytical Methods

6.14.1. Analysis of Plasma A β

6.14.1.1. Placebo-Controlled Period

To evaluate the change in plasma $A\beta$ analytes (including assayed plasma $A\beta_{1-40}$ and $A\beta_{1-42}$) after treatment, an MMRM will be used to compare change from baseline to 71 weeks. This analysis will be done separately for each plasma $A\beta$ parameter. The model for the fixed effects will include terms for the following independent effects: baseline plasma $A\beta$, treatment, visit, and treatment-by-visit interaction. Visit will be considered a categorical variable with values equal to the visit numbers at which plasma $A\beta$ is assessed. The null hypothesis is that the difference in LSM between the LY3314814 (previously known as AZD3293) dose groups and placebo equal zero.

6.14.2. Analysis of CSF Data

6.14.2.1. Placebo-Controlled Period

To evaluate the change in CSF biomarkers (including total CSF $A\beta_{1-40}$, total CSF $A\beta_{1-42}$, CSF total tau, and CSF p-tau from lumbar puncture) after treatment, an ANCOVA will be used. The change from baseline score to the LOCF endpoint during the treatment period will be the dependent variable. The model for the fixed effects will include terms for: baseline CSF and treatment. The null hypothesis is that the difference in LSM between the LY3314814 dose groups versus placebo equal zero. Analyses of additional CSF analytes including RBC and WBC will be done in a similar manner.

Annualized change in CSF biomarkers for each patient will be calculated using the change in CSF at the last post-baseline visit. The annualized change will be compared between the treatment groups with an ANCOVA. The ANCOVA model will include the following independent variables: baseline CSF value and treatment. The null hypothesis is that the difference in LSM between the LY3314814 dose groups and placebo equal zero.

6.14.3. Analyses of Amyloid PET Data

6.14.3.1. Placebo-Controlled Period

The PET images acquired in the study will be processed using previously mentioned methods (Clark et al. 2012). At baseline, standard uptake value ratio (SUVr) will be calculated using as a ratio of the composite summary region that is an average of 6 different cortical regions (anterior cingulate, posterior cingulate, medial orbital frontal, lateral temporal, lateral parietal, precuneus) with whole cerebellum as a reference region. However, post-baseline SUVr values will be calculated using 2 different reference regions whole cerebellum and a correction factor using atlas based white matter (AWM). The SUVr with whole cerebellum will be calculated as a ratio of composite summary region to whole cerebellum as a reference region, similar to the calculation at baseline. The SUVr values using AWM correction factors will be calculated by dividing the composite summary ratio by an AWM correction factor. This correction factor is a

ratio of SUV values of AWM to whole cerebellum from baseline to post-baseline. The complete listing of AV45 regions is provided in **Error! Reference source not found.**.

The change from baseline to the post-baseline visit of the composite summary standard uptake value ratio (SUVr) of AV-45 (amyloid imaging) normalized (based on AVID guidelines) will be done using an analysis of covariance (ANCOVA) model with fixed effects of baseline AV-45 result, and treatment. The null hypothesis is that the difference in LSM between the LY3314814 dose groups versus placebo equal zero.

Annualized change in the composite summary SUVr of AV-45 for each patient will be calculated using the change at the last post-baseline visit. The annualized change will be compared between the treatment groups with an ANCOVA. The ANCOVA model will include the following independent variables: baseline AV-45 value and treatment. The null hypothesis is that the difference in LSM between the LY3314814 dose groups and placebo equal zero.

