#### 10.3.3.6.3. Analysis of Amyloid PET Imaging

Florbetapir PET scans provide an in vivo measurement of deposited amyloid plaques in the brain. Florbetapir cortical composite SUVr correlates with post-mortem assessments of amyloid plaque load (Clark et al. 2012; Joshi et al. 2015). Florbetapir amyloid scans will be performed at screening, 78 and 156 weeks. The change in SUVr between baseline and follow-up scans will be compared across treatment groups and to total exposure to LY3314814.

Change in SUVr will be examined using an ANCOVA model containing terms for baseline SUVr, treatment, and age at baseline. The null hypothesis is that the difference in LSM between

the LY3314814 dose groups and placebo equals zero. Further details regarding the analysis will be provided in the SAP.

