6.2. Adjustments for Covariates

Repeated measures models will include the fixed, categorical effects of treatment, visit (treated as a categorical variable), treatment-by-visit interaction, pooled site, and concomitant AChEI and/or memantine use at baseline (yes/no), as well as the continuous, fixed covariate of baseline, baseline-by-visit interaction and age at baseline.

When an analysis of covariance (ANCOVA) model is used to analyze a continuous efficacy or safety variable, the model will contain the main effects of treatment, pooled site, concomitant AChEI and/or memantine use at baseline (yes/no), and the appropriate baseline value as a covariate.

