6.14.4. Analyses of FDG PET Data

6.14.4.1. Placebo-Controlled Period

The primary analysis of the fluorodeoxyglucose positron emission tomography (FDG PET) scans will follow the established methods of Landau et al (2011). Composite FDG SUVr will be calculated using the following regions: the left and right parietal (angular gyrus), left and right posterior cingulate, and the left and right temporal lobes (Landau et al, 2011). Two composite summary standard uptake value ratios (SUVr) of FDG PET normalized to the pons + vermis will be assessed: (1) Composite Meta and (2) Composite Meta Automated Anatomical Labeling atlas (AAL).

The change from baseline to the post-baseline visit of the composite summary standard uptake value ratio (SUVr) of FDG PET (fluorodeoxyglucose positron emission tomography) will be done using an analysis of covariance (ANCOVA) model with fixed effects of baseline biomarker result, treatment, and baseline biomarker result taken prior to study drug initiation (Yes or No). The null hypothesis is that the difference in LSM between the LY3314814 dose groups versus placebo equal zero.

Annualized change in the composite summary SUVr for each patient will be calculated using the change at the last post-baseline visit. The annualized change will be compared between the treatment groups with an ANCOVA. The ANCOVA model will include the following independent variables: baseline biomarker value, and treatment. The null hypothesis is that the difference in LSM between the LY3314814 dose groups and placebo equal zero.

The analyses described in this section will be repeated in application to the florbetapir (AV-45) perfusion analysis.

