6.14.5. Analyses of Tau PET Data

6.14.5.1. Placebo-Controlled Period

To evaluate the change from baseline in tau imaging parameters, an MMRM analysis will be used to compare change from baseline in SUVr at 78 weeks in the PC Evaluable population. The model will include the fixed, categorical effects of treatment, visit, and treatment-by-visit interaction, as well as continuous effects of baseline SUVr and age at baseline. Visit will be considered a categorical variable with values equal to the visit numbers at which tau imaging is assessed. The null hypothesis is that the difference in LSM between the LY3314814 dose groups and placebo equals zero.

Change from baseline and annualized change from baseline analyses will be conducted on SUVrs computed from the MUBADA region with the bimodal white matter serving as the reference region. The annualized change will be compared between the treatment groups with an ANCOVA in the PC Evaluable population. The ANCOVA model will include the fixed effect of treatment as well as continuous effects of baseline AV-1451 value and age at baseline. The null hypothesis is that the difference in LSM between the LY3314814 dose groups and placebo equal zero.

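### The SAP's amyloid SUVr ANCOVA omits age at baseline, which the protocol specifies, and gives no reason; both tau PET models keep it

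*SAP*

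**What the plan says.** Protocol 10.3.3.6.3 (Analysis of Amyloid PET Imaging) sets the model for change in florbetapir SUVr: "Change in SUVr will be examined using an ANCOVA model containing terms for baseline SUVr, treatment, and age at baseline". It leaves further details to the SAP.

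SAP 6.14.3.1 models the same outcome, change in composite SUVr, with an "analysis of covariance (ANCOVA) model with fixed effects of baseline AV-45 result, and treatment". Its second amyloid model, for annualized change, lists as "independent variables: baseline AV-45 value and treatment". Neither contains age.

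SAP 6.14.5.1 (tau PET) includes "continuous effects of baseline SUVr and age at baseline" in its repeated-measures model, and age is again a covariate in the annualized-change ANCOVA for tau. Age is also in the primary clinical model (SAP 6.12.1.1).

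Protocol 10.3.1 allows changes of analysis method that do not touch a principal feature to be made without an amendment, provided that the SAP and the study report describe both the change and its justification. The SAP's revision history records that the amyloid PET description was revised. It gives no reason, and 6.14.3.1 gives none for the missing age term.

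**The concern.** Brain amyloid burden is a listed secondary biomarker objective (SAP 4.2.2). The protocol names three terms for its model and the SAP names two. Anyone tracing the reported analysis back to the protocol will find that a named covariate has disappeared without explanation.

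The treatment of age also differs inside SAP 6.14. Amyloid and tau PET are both analysed as change in SUVr. Tau keeps age, while amyloid, for which the protocol explicitly asks for age, does not.

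Precision and traceability are at stake. If age predicts SUVr change beyond what baseline SUVr explains, leaving it out makes the intervals around the dose contrasts wider than they need to be.

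**Working it through.** **Step 1. Compare the models term by term.**

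| Outcome | Main protocol | SAP |
|---|---|---|
| Amyloid SUVr, change | baseline, treatment, **age** (10.3.3.6.3) | baseline, treatment (6.14.3.1) |
| Amyloid SUVr, annualized | no model given | baseline, treatment (6.14.3.1) |
| Tau PET, change | separate addendum | baseline, treatment, visit, treatment-by-visit, **age** (6.14.5.1) |
| Tau PET, annualized | separate addendum | baseline, treatment, **age** (6.14.5.1) |
| FDG PET, change | separate addendum | baseline, treatment, indicator for baseline taken before drug start (6.14.4.1) |
| FDG PET, annualized | separate addendum | baseline, treatment (6.14.4.1) |
| CSF, change | plasma Aβ repeated-measures model, no age (10.3.3.6.4, 10.3.3.6.1) | baseline, treatment (6.14.2.1) |
| CSF, annualized | baseline, treatment (10.3.3.6.4) | baseline, treatment (6.14.2.1) |
| vMRI, change and annualized | baseline, treatment (10.3.3.6.2) | baseline, treatment (6.14.6.1) |
| Florbetapir perfusion, change | baseline, treatment (10.3.3.6.5) | FDG analyses repeated (6.14.4.1) |

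Only in the first row does the SAP leave out an age term that the protocol specifies. The annualized amyloid model has no protocol counterpart. The case for age there is consistency with the annualized tau model.

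**Step 2. Size of the precision loss.** The plan states no figure for this, so there is nothing to reproduce. Let r be the partial correlation between age and SUVr change, given baseline SUVr and treatment. It is not in the documents; 0.1 to 0.3 is an assumption. Adding age multiplies residual variance by 1 − r² and the standard error by √(1 − r²).

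| Assumed r | Residual variance multiplied by | Standard error multiplied by | Fall in standard error |
|---|---|---|---|
| 0.1 | 1 − 0.01 = 0.99 | √0.99 = 0.995 | 0.5% |
| 0.2 | 1 − 0.04 = 0.96 | √0.96 = 0.980 | 2.0% |
| 0.3 | 1 − 0.09 = 0.91 | √0.91 = 0.954 | 4.6% |

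**Step 3. Cost of the extra term.** The SAP model estimates four coefficients (intercept, baseline, two dose effects), leaving n − 4 residual degrees of freedom. Age reduces this to n − 5. The estimated residual variance therefore changes by the factor (1 − r²)(n − 4)/(n − 5), which is below 1 when n exceeds 4 + 1/r². That is 4 + 100 = 104 patients for r = 0.1, 4 + 25 = 29 for r = 0.2, and 4 + 11.1, or about 15, for r = 0.3. Chance age imbalance between arms adds a further inflation of order 1/n, ignored here. The documents do not give the number of patients with a follow-up florbetapir scan.

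**Step 4. Bias.** Treatment is randomized, so age is independent of treatment in expectation. Leaving it out does not bias the treatment contrast.

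**The case against.** The strongest reply is that the change is permitted and immaterial. Protocol 10.3.3.6.3 defers details to the SAP, Protocol 10.3.1 allows such changes without an amendment, and the revision history discloses that the amyloid section was revised. After the futility stop, SAP 6.1 says that no test will be read as statistically significant, and 6.1.1 calls all results suggestive or hypothesis-generating. The gain in Step 2 rests on a correlation that nobody has documented. Most of this stands, and it is why the point is minor. It does not supply the justification that Protocol 10.3.1 asks for, and removing a covariate that the protocol names is more than filling in a detail.

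Four stronger readings are tempting, and the documents do not support them.

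- *Age was dropped from all the biomarker models.* The protocol's own vMRI, CSF and perfusion models have no age term, and the main protocol gives no FDG model. Adding age to the CSF and vMRI models would move the SAP away from protocol specifications that also leave age out.
- *All the non-tau ANCOVAs adjust for baseline only.* The FDG change model has "baseline biomarker result, treatment, and baseline biomarker result taken prior to study drug initiation (Yes or No"). Only its annualized model is limited to "independent variables: baseline biomarker value, and treatment".
- *SAP 6.2 requires further covariates in every ANCOVA.* Its rule that "the model will contain the main effects of treatment, pooled site, concomitant AChEI and/or memantine use at baseline (yes/no") plus the baseline value is confined to efficacy or safety variables, and its list contains no age, so it cannot support adding age. Whether it reaches the biomarkers is unclear: Protocol Table 2.3 groups PET, lumbar puncture and MRI with additional efficacy measures, while SAP 6.14 treats them under bioanalytical methods with models of their own.
- *These are all small subsets in which age imbalance matters most.* MRI is scheduled for all patients at Week 78 (Protocol Table 2.2). Follow-up florbetapir PET is limited to patients who entered the study by florbetapir PET, but no subset size is given.

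**Conclusion.** The point holds for the amyloid SUVr change model: the protocol specifies age at baseline, the SAP omits it and gives no reason, and both tau PET models keep it. The mismatch is certain from the text.

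Its statistical effect is small and, on the documents, uncertain. It is a loss of precision with no bias, worth about 0.5% to 5% of the standard error if the partial correlation is 0.1 to 0.3. No stated sample size, power or significance level depends on it, and no decision turns on it now that the results are hypothesis-generating. It is a low-priority correction, worth making because it restores agreement with the protocol at almost no cost. The scope of SAP 6.2 is a matter for clarification only, and adding age to the CSF, FDG and vMRI models is optional.

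**What to change.** In SAP 6.14.3.1, restore age at baseline as a continuous covariate in the change-from-baseline ANCOVA, and add it to the annualized-change ANCOVA so that amyloid and tau are handled alike. If the sponsor prefers to leave age out, the SAP should give the reason, as Protocol 10.3.1 requires. Either way, this should be settled before the final unblinding that the SAP's revision history refers to.

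One sentence in SAP 6.2 could state whether its ANCOVA rule applies to the biomarkers in 6.14.

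The cost is a few words of SAP text and one degree of freedom per model. Age at baseline is already collected and already used in the primary and tau models.

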6.14.4. Analyses of FDG PET Data

6.14.4.1. Placebo-Controlled Period

The primary analysis of the fluorodeoxyglucose positron emission tomography (FDG PET) scans will follow the established methods of Landau et al (2011). Composite FDG SUVr will be calculated using the following regions: the left and right parietal (angular gyrus), left and right posterior cingulate, and the left and right temporal lobes (Landau et al, 2011). Two composite summary standard uptake value ratios (SUVr) of FDG PET normalized to the pons + vermis will be assessed: (1) Composite Meta and (2) Composite Meta Automated Anatomical Labeling atlas (AAL).

The change from baseline to the post-baseline visit of the composite summary standard uptake value ratio (SUVr) of FDG PET (fluorodeoxyglucose positron emission tomography) will be done using an analysis of covariance (ANCOVA) model with fixed effects of baseline biomarker result, treatment, and baseline biomarker result taken prior to study drug initiation (Yes or No). The null hypothesis is that the difference in LSM between the LY3314814 dose groups versus placebo equal zero.

Annualized change in the composite summary SUVr for each patient will be calculated using the change at the last post-baseline visit. The annualized change will be compared between the treatment groups with an ANCOVA. The ANCOVA model will include the following independent variables: baseline biomarker value, and treatment. The null hypothesis is that the difference in LSM between the LY3314814 dose groups and placebo equal zero.

The analyses described in this section will be repeated in application to the florbetapir (AV-45) perfusion analysis.

6.14.5. Analyses of Tau PET Data

6.14.5.1. Placebo-Controlled Period

To evaluate the change from baseline in tau imaging parameters, an MMRM analysis will be used to compare change from baseline in SUVr at 78 weeks in the PC Evaluable population. The model will include the fixed, categorical effects of treatment, visit, and treatment-by-visit interaction, as well as continuous effects of baseline SUVr and age at baseline. Visit will be considered a categorical variable with values equal to the visit numbers at which tau imaging is assessed. The null hypothesis is that the difference in LSM between the LY3314814 dose groups and placebo equals zero.

Change from baseline and annualized change from baseline analyses will be conducted on SUVrs computed from the MUBADA region with the bimodal white matter serving as the reference region. The annualized change will be compared between the treatment groups with an ANCOVA in the PC Evaluable population. The ANCOVA model will include the fixed effect of treatment as well as continuous effects of baseline AV-1451 value and age at baseline. The null hypothesis is that the difference in LSM between the LY3314814 dose groups and placebo equal zero.

6.14.6. Analyses of vMRI Data

6.14.6.1. Placebo-Controlled Period

Analyses of the following volumetric MRI (vMRI) parameters will be conducted (right + left for all but whole brain volume and ventricular volume):

- Hippocampal volume (mm³)
- Entorhinal cortex (mm³)
- Inferior parietal lobe (mm³)
- Isthmus cingulate (mm³)
- Lateral parietal lobe (mm³)
- Medial temporal lobe (mm³)
- Precuneus (mm³)
- Prefrontal lobe (mm³)
- Superior temporal lobe (mm³)
- Atrophy of Total whole brain volume (cm³)
- Enlargement of Ventricular volume (cm³)

All of the above volumes are corrected for intracranial volume. To evaluate the changes in vMRI data after treatment, an ANCOVA model will be used to compare change from baseline to 78 weeks in the PC Evaluable population. The change from baseline to the endpoint visit will be the dependent variable. The model for the fixed effects will include terms for the following independent effects: baseline vMRI value and treatment. The null hypothesis is that the difference in LSM between the LY3314814 dose groups and placebo equal zero.

Annualized change in vMRI for each patient will be calculated using the change in vMRI at the last post-baseline visit. The annualized change will be compared between the treatment groups with an ANCOVA model. The ANCOVA model will include the following independent variables: baseline vMRI value and treatment. The null hypothesis is that the difference in LSM between the LY3314814 dose groups and placebo equal zero.

6.15. Subgroup Analyses

To assess the effects of various demographic and baseline characteristics, subgroup analyses will be performed for the primary endpoint for the Placebo-Controlled period based on the following variables:

- Age ≥ 55 and < 72 or ≥ 72 and < 85
- APOE4 carrier status (carrier $[\epsilon 2/\epsilon 4, \epsilon 3/\epsilon 4, \epsilon 4/\epsilon 4]/\text{non-carrier})$
- Region US or OUS

The primary outcome measure for the Placebo-Controlled period will be modeled using a mixed model repeated measures (MMRM) approach. This general model will include terms for baseline, treatment, visit, concomitant AChEI/memantine use at baseline (yes/no), age (except when age is the subgroup being assessed), treatment by visit, subgroup by treatment, subgroup by visit, and treatment by visit and subgroup. Redundant terms will be dropped from the model in cases where the subgroup of interest overlaps with this general model.

All subgroup analyses presented will be exploratory.

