# 2. Schedule of Activities

Table 2.1. Study Schedule, Protocol I8D-MC-AZET, Visit 1: Preliminary Screening and Screening

Days relative to Study Medication Start	Visit 1 (-60 days to baseline measures)
Preliminary Screening	
Entry and Administrative	
Abbreviated (or full) Informed Consent a - participant and study partner	X
Patient number assigned via IxRS	X
Demographics	X
Entry Diagnostics (Study Partner) b	
AD8	X
CDR c	X
Entry Diagnostics (Patient) b	
MMSE	X
CDR c	X
Screening	
Entry and Administrative	
Full Informed Consent a - participant and study partner	X
Medical /psychiatric History	X
Concomitant treatments	X
Inclusion/exclusion criteria	X
Entry Diagnostics (Patient)	
Amyloid PET (+/- perfusion) d	
$OR^e$	X
Lumbar puncture f	
Safety Measures	
MRI d,f	X
12-Lead ECG g	X
Vital signs h	X
Height	X
Body weight	X
Adverse events	X
Laboratory Specimens	
Laboratory tests (see Appendix 2)	X
Clinical Exams	
Physical, neurological examinations	X
Comprehensive eye examination i	X
Skin examination j	X

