### General Criteria

- [1] Provision of signed and dated informed consent form (ICF) from patient (or legal representative if required) and from study partner prior to any study-specific procedures being performed
- [2] Male or female, aged 55 to 85 years inclusive at the time of signing ICF

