#### 10.3.6.2. Subgroup Analyses

To assess the effects of various demographic and baseline characteristics, subgroup analyses of the primary endpoint for the Placebo-Controlled period, ADAS-Cog13, will be performed based on the following variables: gender, age, race, APOE4 carrier status, country, concomitant AD therapy, compliance with investigational product, and reason for discontinuation. The specific grouping of patients based on these variables will be outlined in the SAP. All subgroup analyses will be considered secondary analyses.

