6.8. Subject Characteristics

Baseline subject characteristics will be summarized for the Randomized population by treatment group and overall.

Summaries will include descriptive statistics for continuous and categorical measures. Fisher's Exact test will be used for treatment group comparisons of categorical data. For continuous data, analysis of variance (ANOVA), with independent factors for treatment, will be used. Subject characteristics that will be summarized include:

- age (continuous and categorized into 55-64, 65-74, and 75+)
- gender
- race (and ethnicity)

- height
- body weight
- body mass index (weight (kg) / [height (m)]2)
- region
- tobacco use
- alcohol use
- caffeine use
- years of education
- work status
- having 1 or more first degree relatives with AD
- AChEI and/or memantine use at baseline
- time since diagnosis
- amyloid inclusion method (PET, CSF, historical PET)
- Mini Mental State Examination (MMSE) score at Visit 1
- Baseline severity of impairment as measured by ADAS-Cog13, ADAS-Cog11 ADCS-ADL total score and instrumental (ADCS-iADL) and basic subscores (ADCS-bADL), iADRS, CDR Sum of Boxes, RBANS, NPI, RUD-Lite, EQ-5D Proxy, and FAQ.
- APOE4 genotype ($\varepsilon 2/\varepsilon 4$, $\varepsilon 3/\varepsilon 4$, $\varepsilon 4/\varepsilon 4$, no $\varepsilon 4$) and carrier status (carrier [$\varepsilon 2/\varepsilon 4$, $\varepsilon 3/\varepsilon 4$, $\varepsilon 4/\varepsilon 4$], noncarrier [$\varepsilon 3/\varepsilon 3$, $\varepsilon 2/\varepsilon 2$, $\varepsilon 3/\varepsilon 2$])

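### The SAP's upper age subgroup stops below 85, so eligible patients aged 85 belong to neither age group

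*SAP*

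**What the plan says.** Three statements bear on this point.

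- **Eligibility.** Protocol Section 6.1, criterion 2, reads "Male or female, aged 55 to 85 years inclusive at the time of signing ICF". Both ends are included, and age is fixed at consent.
- **Subgroup definition.** SAP Section 6.15 states that "subgroup analyses will be performed for the primary endpoint for the Placebo-Controlled period based on the following variables", and the first variable listed is "Age ≥ 55 and < 72 or ≥ 72 and < 85".
- **Where the cut-offs come from.** Protocol Section 10.3.6.2 names age as a subgroup variable but gives no boundaries: "The specific grouping of patients based on these variables will be outlined in the SAP". The line in SAP 6.15 is therefore the only definition.

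Elsewhere the SAP treats the top of the age range differently. The baseline summaries in Section 6.8 use "age (continuous and categorized into 55-64, 65-74, and 75" and above, an open category that includes age 85.

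**The concern.** The upper age group has a strict upper limit at an age that the protocol explicitly admits. A patient aged 85 at consent satisfies criterion 2, can be randomized, and then meets neither half of the age definition.

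The model in SAP 6.15 contains subgroup-by-treatment, subgroup-by-visit and three-way terms. Under the usual handling of a missing class variable, a patient without a subgroup value is left out of such a model. Read literally, the rule removes the oldest randomized patients from the analysis meant to describe the effect by age, and the two age groups no longer add up to the evaluable population.

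A programmer could instead put these patients in the upper group, but that departs from the written rule. Two programmers working independently could reasonably disagree, and the choice should not be left until after unblinding.

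**Working it through.** The plan states no figure on this point, so there is none to reproduce. The check sets every eligible age against the two intervals.

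**Inputs**

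- Eligible ages: 55 to 85, both included (Protocol 6.1, criterion 2).
- Lower group: ≥ 55 and < 72. Upper group: ≥ 72 and < 85 (SAP 6.15).
- Planned number randomized: 1899 (SAP 5.2).
- Screening window: "Visit 1 (-60 days to baseline measures" (Protocol Section 2, Table 2.1).

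**Step 1: coverage as written, in whole years**

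| Set | Ages | Count |
|---|---|---|
| Eligible | 55–85 | 85 − 55 + 1 = 31 |
| Lower group | 55–71 | 71 − 55 + 1 = 17 |
| Upper group | 72–84 | 84 − 72 + 1 = 13 |
| Neither | 85 | 31 − 17 − 13 = 1 |

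**Step 2: coverage under two corrections**

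| Upper group | Age 85 covered | Age 86 covered |
|---|---|---|
| ≥ 72 and ≤ 85 | yes | no |
| ≥ 72, no upper limit | yes | yes |

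Age 86 matters because eligibility is judged at consent, while SAP 6.15 does not say on which date subgroup age is taken. The main model uses age at baseline (SAP 6.12.1.1). With up to 60 days between screening and baseline, a patient who consented at 85 can be 86 at baseline. If baseline age is used, the gap as written also catches a patient who consented at 84 and turned 85 during screening.

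**Step 3: how many patients**

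Neither document gives an age distribution, so the share aged 85 is an assumption. Number affected = 1899 × share:

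| Assumed share aged 85 | Patients |
|---|---|
| 0.5% | 1899 × 0.005 ≈ 9 |
| 1% | 1899 × 0.01 ≈ 19 |
| 2% | 1899 × 0.02 ≈ 38 |
| 3% | 1899 × 0.03 ≈ 57 |

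The base of 1899 is the planned randomized number. The analysis set needs a baseline and at least one post-baseline result (SAP 6.6), so the number with usable data can only be the same or smaller for a given number randomized.

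**Step 4: does another analysis fill the gap?**

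In the primary model (SAP 6.12.1.1) age enters only as a main effect, with no age-by-treatment term. Subgroup analyses of adverse events have been removed (SAP Section 3, item 27). The analysis in 6.15 is the only planned look at treatment effect by age.

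**The case against.** The strongest reply is that almost nothing depends on this line. SAP 6.15 says that "All subgroup analyses presented will be exploratory". This SAP version was written after the study was stopped for futility, and Sections 6.1 and 6.1.1 say that no test will be read as significant and that all results are only suggestive. Patients aged 85 stay in the primary analysis and in the APOE4 and region subgroups. Sample size and alpha are untouched. All of this is correct, and it limits the weight of the point.

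A second reply is that this is a drafting slip and that the program may simply split at 72, which would place everyone. That may be so. The open top category in SAP 6.8 suggests no intention to exclude anyone. The loss of patients is therefore conditional on literal programming. The written rule still needs correcting, because a program that splits at 72 would not match it.

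Third, the count is assumed. That also stands: the figures show scale only, and the true number is unknown and probably small.

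Fourth, subgroup counts need not add up in any case. APOE4 testing can be barred by national law (Protocol 9.7.1), so that subgroup may also be incomplete. But that gap comes from data that could not be collected, whereas age is needed to establish eligibility.

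A misprinted symbol is possible but unlikely. The greater-or-equal sign appears twice in the same line, and the less-or-equal sign appears in SAP Appendices 3 and 4.

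**Conclusion.** The point holds. SAP 6.15 and inclusion criterion 2 disagree at age 85, and neither document contains a rule that repairs it. One of 31 eligible whole-year ages has no subgroup.

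Its importance is minor. It affects one exploratory model of ADAS-Cog13 in a study stopped for futility, and no decision rests on it. If 1% to 2% of 1899 patients were aged 85, about 19 to 38 would be affected; over 0.5% to 3% the range is about 9 to 57. These shares are assumptions. The mismatch itself does not depend on them, and the loss of patients from the model depends on the rule being programmed as written.

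**What to change.** In SAP 6.15, define the age groups as ≥ 55 and < 72, and ≥ 72 with no upper limit. Closing the interval at ≤ 85 is the weaker choice: it would again leave out a patient who turned 86 between consent and baseline if baseline age is used.

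In the same line, state the date at which subgroup age is taken. Age at baseline would match the covariate in the main model.

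The cost is one line in the SAP and one condition in the program, with no new data and no effect on any other analysis. SAP Section 3 says that version 3 is to be approved before final unblinding, so the correction belongs in that approval.
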